4. OBJECTIVE(S) AND ENDPOINT(S)

Objectives	Endpoints
Primary	

To examine the effect of RVT-1401 on proportion of responders (defined as Hb level $\geq 10\text{g/dL}$ with at least a $\geq 2\text{ g/dL}$ increase from baseline without rescue therapy or blood transfusions in the previous two weeks)
 
To assess the safety and tolerability of RVT-1401 in subjects with WAIHA
	
Proportion of responders at week 13
 
Assessment of safety and tolerability by analysis of adverse event (AE) data and changes from baseline in vital signs, ECGs, and clinical laboratory values

Secondary	

To examine the effect of RVT-1401 on change in Hb levels
	
Change from baseline in Hb levels

To examine the effect of RVT-1401 on time to response
	
Time to response

To examine the effect of RVT-1401 on change in hematocrit levels
	
Change from baseline in hematocrit levels

To examine the effect of RVT-1401 on proportion of participants with Hb levels in the normal range
	
Proportion of participants with Hb levels in the normal range at week 13

To examine the effect of RVT-1401 on time to achieving Hb levels in the normal range
	
Time to achieving Hb levels in the normal range

To examine the effect of RVT-1401 on change in fatigue
	
Change from baseline in FACIT-F score

To examine the effect of RVT-1401 on change in dyspnea
	
Change from baseline in Medical Research Council (MRC) breathlessness scale

To examine the effect of RVT-1401 on change in health-related quality of life
	
Change from baseline in EQ-5D-3L score

To assess the change in serum levels of total IgG & IgG subclasses (I-IV)
	
Change from baseline in levels of total IgG & IgG subclasses (I-IV)

To examine RVT-1401 PK following repeated doses in patients with WAIHA
	
Concentration of RVT-1401 pre-dose (C_{trough})

To assess the changes in LDH, bilirubin,
	
Change from baseline in LDH, bilirubin, and

haptoglobin
 
To measure anti-RVT-1401 antibodies following repeated doses in patients with WAIHA
	
haptoglobin
 
Immunogenicity determined by change from pre-dose in anti-RVT-1401 antibodies, and characterization of any anti-RVT-1401 to confirm neutralization potential

Exploratory
	
	

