6.9.2. Management of Rescue Therapy

Rescue therapy during the first 8 weeks of the Treatment Period is permitted for participants with haemoglobin levels <7.0 g/dL or in the presence of signs/symptoms of myocardial ischemia, hypoxia, or TIA/stroke. Participants requiring rescue therapy after the Week 8 visit will be discontinued and an early withdrawal visit scheduled.

Blood Transfusion

The date, time, and number of units transfused should be recorded, along with the results of cross-match testing. Follow-up hemoglobin should be measured with 12 hours of the end of the transfusion. Hemoglobin values will be censored from efficacy analyses for the 2 weeks following a blood transfusion.

Prednisone/Prednisolone

Prednisone/prednisolone rescue (up to a 50% increase from baseline for up to 5 days), is permitted as per the rescue therapy guidelines (Section 6.9.2). The date, time, and dose should be recorded. Hemoglobin values will be censored from efficacy analyses for the 2 weeks following the last dose of prednisone/prednisolone rescue.

Dexamethasone

High dose dexamethasone (up to 40 mg daily for up to 4 days) is permitted as per the rescue therapy guidelines (Section 6.9.2). The date, time, and dose should be recorded. Hemoglobin values will be censored from efficacy analyses for the 2 weeks following the last dose of dexamethasone rescue.

IVIg and Plasma Exchange

Due to the mechanism of action for RVT-1401, the use of IVIG and Plasma exchange are not allowed.

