10.3.3. Secondary Endpoints for Efficacy

For each of the continuous secondary endpoints, the actual value, change from baseline and percentage change from baseline for all secondary endpoints will be summarized by visit and treatment group using the n, mean, SD, median, first and third quartiles, minimum, and maximum values. The comparison of the active arms (separately) will be performed using a Mixed Model for Repeated Measures (MMRM)/ Analysis of Covariance model with treatment, Visit, and baseline value in the model. The least square means of the treatment difference, standard errors, 95% CI and p-value for the treatment will be presented at each visit. A 2-sided alpha of 0.05 will be used to determine statistical significance for Treatment. If deemed appropriate, the two active arms may be combined to evaluate any treatment effect for the changes from the baseline.

For categorical secondary endpoints, the number of participants who meet the endpoint and the percentage will be summarized. The percentage will be calculated using those participants who had a value at the time point. Statistical testing may be performed between the two treatments using a Fishers Exact Test. If deemed appropriate, the two active arms may be combined to evaluate any treatment effect for the shift from the baseline.

The analyses of the secondary endpoints will be performed on ITT based on all available data, without using any imputation method for missing data.

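### The two-week post-rescue censoring rule names hemoglobin only, so under Protocol 10.3.3 a hematocrit from the same draw would stay in the by-visit analysis

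*Protocol*

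**What the plan says.** Protocol 6.9.2 states the censoring rule three times.

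- After transfusion: "Hemoglobin values will be censored from efficacy analyses for the 2 weeks following a blood transfusion".
- After prednisone or prednisolone: "Hemoglobin values will be censored from efficacy analyses for the 2 weeks following the last dose of prednisone/prednisolone rescue".
- After dexamethasone: "Hemoglobin values will be censored from efficacy analyses for the 2 weeks following the last dose of dexamethasone rescue".

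On timing, the same section says "Rescue therapy during the first 8 weeks of the Treatment Period is permitted", and "Participants requiring rescue therapy after the Week 8 visit will be discontinued and an early withdrawal visit scheduled".

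Protocol section 4 lists "Change from baseline in hematocrit levels" as a secondary endpoint, alongside change in hemoglobin and change in LDH, bilirubin and haptoglobin. Protocol 10.3.3 analyses continuous secondary endpoints by visit, with descriptive summaries and an MMRM/ANCOVA, and allows the two dose cohorts to be pooled to look for a change from baseline. Its data rule is "The analyses of the secondary endpoints will be performed on ITT based on all available data", with no imputation and no exclusion for rescue or transfusion.

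The primary responder definition in section 4 carries its own condition, "without rescue therapy or blood transfusions in the previous two weeks".

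SAP Version 3.0, which governs the Cohort 1 report, is confined to listings and has removed derived variables (SAP section 1). Laboratory values are listed by visit (SAP 9.3); rescue therapy and procedures are listed separately (SAP 9.4). The SAP repeats no censoring rule and provides no flag for values taken after rescue.

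**The concern.** Section 6.9.2 treats a hemoglobin value as unfit for efficacy analysis for two weeks after transfusion or steroid rescue. Transfused red cells raise hematocrit by the same mechanism, and Protocol 8.3.4 puts both measures in one hematology panel. No reason is given for handling them differently, and no other section extends the rule. At one visit, from one draw, the protocol would discard the hemoglobin and analyse the hematocrit.

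Both cohorts receive active drug and neither is randomized, so nothing in the change-from-baseline analysis separates a transfusion effect from a drug effect. In the comparison of doses, the retained values would favour whichever cohort needed more transfusion. Two endpoints that track the same quantity could then disagree only because of a data rule.

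**Working it through.** The documents state no figure for this point, so there is none to reproduce. The check has three parts: which visits the gap reaches, how large the effect could be, and what deleting the values would do.

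**1. Visits reached**

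Inputs: hematology and chemistry share one schedule row, at Weeks 1, 2, 3, 4, 5, 7, 9, 11, 13, 14, 16 and 20 and at early withdrawal (Protocol 8.1). The visit window is ±1 day through Week 12 and ±2 days from Week 13. Steroid rescue lasts up to 5 days (prednisone/prednisolone) or 4 days (dexamethasone) (Protocol 6.9.2).

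Formulas: nominal visit day = 7 × (week − 1) + 1; window end = last rescue day + 14.

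- The Week 8 visit is day 7 × 7 + 1 = 50, or 51 with the visit window.
- Transfusion at that visit: window ends on day 50 + 14 = 64, or 65.
- A 5-day steroid course starting then: last dose day 54 or 55, window ends on day 68 or 69.
- A 4-day course: last dose day 53 or 54, window ends on day 67 or 68.
- Week 9 is day 57, so it is inside. Week 11 is day 71, earliest 70, so it is outside. Week 13 is day 85, earliest 83, so it is well outside.

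The scheduled post-baseline visits within reach are therefore Weeks 2, 3, 4, 5, 7 and 9. Rescue after the Week 8 visit leads to discontinuation, so it can affect the early-withdrawal value.

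For a transfusion on each of days 1 to 50, counting scheduled draws in the following 14 days on nominal days:

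- days 1 to 21 catch two draws (21 days);
- days 22 to 50 catch one draw (29 days).

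Each transfusion thus touches one or two scheduled hematocrit values.

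**2. Size for hematocrit (illustration; inputs assumed)**

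Shift in one visit's cohort mean = participants transfused × units × points per unit ÷ number in cohort.

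Assumptions: 8 per cohort (half of the planned 16, as the split is not readable), one participant given 2 units, and 3 hematocrit points per unit (range 2 to 4).

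- Central: 1 × 2 × 3 ÷ 8 = +0.75 points.
- Range: 1 × 2 × 2 ÷ 8 = +0.5, to 1 × 2 × 4 ÷ 8 = +1.0.

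This applies to a single visit's mean.

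**3. What deletion would do (illustration; inputs assumed)**

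Seven participants change by +3 points. The eighth would have changed by −6 but is raised to 0 by 2 units at 3 points each.

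- Mean without any transfusion effect: (7 × 3 − 6) ÷ 8 = 1.875.
- Transfused value kept: (7 × 3 + 0) ÷ 8 = 2.625, a bias of +0.75.
- Transfused value deleted: (7 × 3) ÷ 7 = 3.0, a bias of +1.125.

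Deletion raises a descriptive mean further than retention whenever the transfused value is still below the mean of the others.

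**The case against.** The strongest reply is that this analysis is not going to be run. A reader might infer that transfused hematocrits will be reported as drug effect in Cohort 1. The SAP does not support that: Version 3.0 plans no mean, change from baseline, model or test for hematocrit or the hemolysis markers. SAP section 8 names only FACIT-F, MRC and EQ-5D-3L, and hematocrit appears only among the safety laboratory listings. This stands, and it confines the analysis problem to Protocol 10.3.3, which would matter if the study resumed under the protocol text.

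A second reply is that removing values from the sickest participants does not cure the bias and can enlarge it. The arithmetic above bears this out. But the protocol has already chosen removal for hemoglobin, so the argument calls for a summary with the values included as well. It does not justify opposite rules for two measures from one sample.

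Third, outside acute symptoms, rescue requires hemoglobin below 7.0 g/dL, while entry requires only below 10 g/dL. Many transfused participants will have fallen below baseline first, so transfusion may make them look less worsened rather than improved. This also stands; the retained hematocrit is still higher than it would have been.

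Fourth, with five subjects a reader can compare the rescue and laboratory listings by hand. That is possible, but it leaves each reader to rebuild the two-week window, which a flag would do once and consistently.

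**Conclusion.** The inconsistency is real, and it lies in the protocol. All three censoring statements in 6.9.2 cover hemoglobin only, and 10.3.3 would keep hematocrit from the same draws. The reach is limited to scheduled Weeks 2, 3, 4, 5, 7 and 9 and early-withdrawal visits. The illustrated +0.75 points (0.5 to 1.0) rests wholly on assumed cohort size, units and points per unit.

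Two further readings go beyond the documents. The primary endpoint is not exposed: its definition excludes rescue and transfusion in the preceding two weeks, and permitted rescue does not reach Week 13. Nor can LDH, bilirubin and haptoglobin be said to be biased towards benefit, because the documents do not determine a direction for them.

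For the Cohort 1 report, the remaining issue is that values taken after transfusion or rescue are listed without a mark.

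**What to change.** 1. In Protocol 6.9.2 and 10.3.3, apply to hematocrit the same two-week analysis rule as hemoglobin, with the same start and end for transfusion and for each steroid rescue. Report by-visit summaries with and without the in-window values, because exclusion can itself raise a descriptive mean.
2. For LDH, bilirubin and haptoglobin, report by-visit results with and without in-window values rather than assuming a direction.
3. In the Cohort 1 listings, flag every hemoglobin, hematocrit, LDH, bilirubin and haptoglobin value inside a rescue or transfusion window.

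The cost is a short addition to the analysis text, a second set of by-visit summaries if the protocol analysis is run, one listing flag, and about one or two scheduled hematocrit values lost from the main analysis per transfusion. This changes analysis rules only; clinical management is untouched.

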6.9.3. Other Management Criteria

For an individual study participant, medical monitor notification criteria include, but are not limited to:

- Severe signs or symptoms, or significant changes in any of the safety assessments, that put the safety of the individual at risk (e.g. laboratory tests or vital signs, etc.) as judged by the Investigator.
- Initiation of rescue therapy (see Section 6.9.2)

6.10. Participant and Study Completion

A completed participant is one who has completed all phases of the study including the follow-up visits.

The end of the study is defined as the last participant's last visit.

7. STUDY TREATMENT

7.1. Investigational Product and Other Study Treatment

Investigational Product

Study Treatment Name:	RVT-1401
Manufacturer:	
Dosage formulation:	Sterile solution for injection.
Unit dose strength(s)/Dosage level(s):	680 mg: 2 mL RVT-1401 in two syringes for a total of 4 mL 340 mg: 2 mL RVT-1401 in one syringe for a total of 2 mL
Route of Administration	SC injection
Dosing instructions:	The detailed methods are indicated in the Pharmacy Manual. Participants will be closely monitored for reactions for up to 1 hr post-dose before they leave the clinic.
Dose Preparation	The preparation procedure and expiry details will be included in the Pharmacy manual/product label.

7.2. Treatment Assignment

Participants will receive either open-label RVT-1401 680 mg/weekly or 340 mg/weekly treatment for up to a maximum of 12 weeks.

7.3. Blinding

This is an open-label study.

7.4. Packaging and Labeling

RVT-1401 will be supplied to the study site as a sterile liquid formulation with a nominal fill of at least 1 mL in Nuova Ompi 2R clear glass vials with a flip-off cap. The solution is clear to slightly yellow, essentially free of visible particles, for SC administration.

Doses will be prepared by the pharmacist or designee with a label that includes at a minimum the study number, participant number, kit number and vial number. Doses are administered to participants by clinic staff or designee.

See Pharmacy Manual for exact instructions on dose preparation.

All labels will meet all local applicable requirements and Annex 13 of Good Manufacturing Practices: Manufacture of investigational medicinal products (July 2010) and/or other local regulations as applicable.

7.5. Preparation/Handling/Storage/Accountability

A description of the methods and materials required for preparation will be detailed in the pharmacy manual.

- Only participants enrolled in the study may receive study treatment and only authorized site staff may prepare, handle, supply or administer study treatment. All study treatments must be stored in a secure environmentally controlled and monitored (manual or automated) area in accordance with the labelled storage conditions with access limited to the Investigator and authorized site staff.
- While the Investigator is ultimately responsible, study treatment accountability, reconciliation, and record maintenance (i.e. receipt, reconciliation and final disposition records) can be designated to the Pharmacist or other designee.
- Under normal conditions of handling and administration, study treatment is not expected to pose significant safety risks to site staff. In the case of unintentional occupational exposure notify the monitor, Medical Monitor and/or the Sponsor study contact.
- A Material Safety Data Sheet (MSDS)/equivalent document describing occupational hazards and recommended handling precautions either will be provided to the Investigator, where this is required by local laws, or is available upon request from the Sponsor.

7.6. Compliance with Study Treatment Administration

The individual dose for a participant is prepared by a Pharmacist, licensed Pharmacy Technician, or designee. The preparation of the dose will be reviewed and confirmed by a second member of the study site staff.

The date and time of each dose administered along with the location of each injection will be recorded in the source documents. The location of each injection and study participant identification will be confirmed at the time of dosing by a member of the study site staff other than the person administering the study drug.

7.7. Treatment of Study Treatment Overdose

An overdose is defined when a participant receives >680 mg in a single visit. The Sponsor does not recommend specific treatment for an overdose.

In the event of an overdose the Investigator or treating physician should:

- contact the Medical Monitor immediately,
- closely monitor the participant for AEs/SAEs and laboratory abnormalities.
- obtain a plasma sample for PK analysis within 2 days from the date of the last dose of study treatment if requested by the Medical Monitor (determined on a case-by-case basis)
- document the quantity of the excess dose as well as the duration of the overdosing in the eCRF

Decisions regarding dose interruptions or modifications will be made by the Investigator in consultation with the Medical Monitor based on the clinical evaluation of the participant.

7.8. Treatment After the End of the Study

Participants will not receive any additional treatment with the study treatment from the Sponsor after completion of the study because the long-term safety and efficacy of RVT-1401 have not been established.

The Principal Investigator is responsible for ensuring that consideration has been given to the post-study care of the participant's medical condition.

7.9. Concomitant Medications and Non-Drug Therapies

Any concomitant medication should be recorded in the study records, including the doses administered, the dates and times of administration and the reason for administration.

Refer to the study inclusion and exclusion criteria (Section 6.2 and Section 6.3) and the study manual for a list of permitted and prohibited medications.

8. STUDY ASSESSMENTS AND PROCEDURES

Protocol waivers or exemptions are not allowed with the exception of immediate safety concerns. Therefore, adherence to the study design requirements, including those specified in the Time and Events Table, are essential and required for study conduct.

This section lists the procedures and parameters of each planned study assessment. All blood draws and rating scale assessments should be completed pre-dose (on dosing days). The timing of each assessment is listed in the Time and Events Table, Section 8.1.

The following points must be noted:

- The IRB/IEC will be informed of any safety issues that require alteration of the safety monitoring scheme or amendment of the Informed Consent Form.
- The total blood volume collected will be specified within the ICF.

8.1. Time and Events Table

Study Timepoint (Weeks)	Screening ¹	Treatment Period (Weeks)												Follow-up Period (Weeks)				Early Withdrawal Visit
	Within 30 days	1 (B/L)	2	3	4	5	6	7	8	9	10	11	12	13	14	16	20	
Time Window (days)			+/-1 day	+/-1 day	+/-1 day	+/-1 day	+/-1 day	+/-1 day	+/-1 day	+/-1 day	+/-1 day	+/-1 day	+/-1 day	+/-2 days	+/-2 days	+/-2 days	+/-2 days	
Informed consent	X																	
Inclusion/exclusion criteria	X	X																
Demographics and medical history ⁹	X																	
Height	X																	
Body weight	X	X																
Complete physical examination	X	X																
Brief physical examination																		X
Vital signs ²	X	X	X	X	X	X	X	X	X	X	X	X	X	X	X	X	X	X
12-lead Electrocardiogram ²	X	X			X					X			X					X
Pregnancy test ³ (females)	X	X	X		X		X		X		X		X	X				X
Viral Serology	X																	
Vaccine Titers ²		X												X				X
QuantiFERON® – TB GOLD	X																	
Urinalysis ^{2, 4}	X	X		X		X		X		X		X		X		X	X	X
Blood chemistry and hematology ^{2, 8}	X	X	X	X	X	X		X		X		X		X	X	X	X	X
Fasting Lipid Panel ²		X												X				X
Serum complement (CH50, C3) ²		X		X		X		X		X		X		X		X	X	X
Immunoglobulins (IgM, IgA) ²		X		X		X		X		X		X		X		X	X	X

Immunovant Sciences GmbH RVT-1401-2003, Amendment 2 Version 3.0

Study Timepoint (Weeks)	Screening ¹	Treatment Period (Weeks)												Follow-up Period (Weeks)				Early Withdrawal Visit
	Within 30 days	1 (B/L)	2	3	4	5	6	7	8	9	10	11	12	13	14	16	20	
Time Window (days)			+/-1 day	+/-1 day	+/-1 day	+/-1 day	+/-1 day	+/-1 day	+/-1 day	+/-1 day	+/-1 day	+/-1 day	+/-1 day	+/-2 days	+/-2 days	+/-2 days	+/-2 days	
RVT-1401 PK sampling ²		X	X	X	X	X	X		X		X		X	X				X
Total IgG ^{2,6}	X	X	X	X	X	X	X		X		X		X	X	X	X	X	X
Immunoglobins (IgG subclasses) ²		X		X			X		X		X		X		X	X	X	X
Anti- RVT-1401 antibody ^{2,5}		X		X		X			X					X			X	X
NAb Assessment ²		X		X		X			X					X			X	X
Drug administration		X	X	X	X	X	X	X	X	X	X	X	X					
Injection Site Reaction ⁷		X	X	X	X	X	X	X	X	X	X	X	X					
FACIT-F Scale ²		X		X		X		X		X		X		X		X	X	X
MRC Breathlessness Scale ²		X		X		X		X		X		X		X		X	X	X
EQ-5D-3L ²		X				X				X				X		X	X	X
Satisfaction Questionnaire														X				X
Adverse events	X	X	X	X	X	X	X	X	X	X	X	X	X	X	X	X	X	X
Concomitant medication	X	X	X	X	X	X	X	X	X	X	X	X	X	X	X	X	X	X

1. Screening can take place over multiple days.
2. Assessments collected on dosing days will be collected pre-dose.
3. Pregnancy tests will be collected pre-dose (via urine dipstick) on dosing days where specified. Serum pregnancy tests should be collected at screening and the final follow up visit.
4. Microalbumin/creatinine ratio at baseline, week 13, and week 20 only.
5. Participants with treatment emergent positive results (change from baseline) for anti- RVT-1401 antibody at Week 20 will be requested to return at approximately 6, 9, and 12 months post-dose for additional samples or until their result is no longer positive. However, for purposes of safety follow-up and database lock participation ends at the Week 20 visit.
6. Two samples for IgG will be collected: one will be sent to the central lab for safety monitoring, while the other sample will be sent to Intertek as the PD endpoint.
7. Local injection site reactions will be assessed at approximately 10 minutes post dose.

Immunovant Sciences GmbH RVT-1401-2003, Amendment 2 Version 3.0

8. Hematology, HbA1c and [REDACTED] will be drawn for site local laboratory analysis, at minimum, and results collected in the instance where central laboratory samples are received hemolyzed. If other central laboratory tests are received hemolyzed, the local result will be captured in the eCRF.
9. History of WAIHA and prior WAIHA treatments will be captured in the eCRF.

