5. STUDY DESIGN

5.1. Overall Design

This is a Phase 2, non-randomized, sequential, open-label study to investigate the safety, tolerability, PK, PD, and efficacy of RVT-1401 (680 mg/weekly and 340 mg/weekly) in patients with WAIHA. The study design is illustrated in Section 5.2.

[figure not shown]
Two cohorts of participants will be enrolled in a non-randomized sequential approach. Participants will be enrolled into Cohort 1 (680 mg/weekly) first followed by Cohort 2 (340 mg/weekly). In the Phase I healthy volunteer study, both dosing regimens were well tolerated (Section 3.3.3). Since 680 mg/weekly has the greater likelihood of demonstrating clinical efficacy, this dosing regimen will be studied in Cohort 1.

Following the initial dose at the Baseline Visit (Week 1, Day 1), study visits will occur weekly throughout the treatment period. Following the final dose at Week 12, visits will occur weekly through Week 14 and then at Week 16 and Week 20. Safety, PK, PD, and clinical assessments will be collected throughout the study. Refer to Section 8.1, Time and Events Table.

Optional home visits will be offered to collect (at a minimum) blood samples, vital signs, and to review adverse events and concomitant medications.

Each participant will participate in the study for up to approximately 24 weeks: up to a 4-week screening period, a 12-week treatment period, and an 8-week follow up period.

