8.3.4. Clinical Safety Laboratory Assessments

All protocol required laboratory assessments must be conducted in accordance with a study manual or Laboratory Manual, and Protocol Time and Events Table (Section 8.1). Laboratory requisition/order forms must be completed, and samples must be clearly labelled with the participant number, protocol number, site/center number, and visit date. Details for the preparation and shipment of samples will be provided by the laboratory and are detailed in the study manual or the laboratory manual. Investigators will also

refer to their local institution for samples being analysed by the local laboratory. Reference ranges for all safety parameters will be provided to the site by the laboratory responsible for the assessments.

If additional non-protocol specified laboratory assessments are performed at the institution's local laboratory and result in a change in participant management or are considered clinically significant by the Investigator (e.g., SAE or AE or dose modification) the results must be recorded.

Central laboratory results will be prioritized except where specific test results are not available due to sample hemolysis as specified in the Time and Events (Section 8.1). In these instances, results from site local laboratories will be collected in the eCRF.

Laboratory sample parameters are listed below:

Hematology

	RBC Indices:	Automated WBC Differential:
Platelet Count		
Red Blood Cell (RBC) Count	Mean corpuscular volume (MCV)	Neutrophils
White Blood Cell (WBC) Count (absolute)	Mean corpuscular hemoglobin (MCH)	Lymphocytes
Reticulocyte Count	Mean corpuscular hemoglobin concentration (MCHC)	Monocytes
Hemoglobin		Eosinophils
Hematocrit		Basophils
Haptoglobin		

Clinical Chemistry

Blood urea nitrogen (BUN)	Potassium	AST (SGOT)	Total (TBL) and direct bilirubin
Creatinine	Chloride	ALT (SGPT)	Uric Acid
Total Protein	Total carbon dioxide (CO ₂)	Gamma glutamyltransferase (GGT)	Albumin
Sodium	Calcium (corrected)	Alkaline phosphatase (ALP)	Lactic acid dehydrogenase (LDH)
Serum complement (CH50, C3)	Immunoglobulin M (IgM)	Immunoglobulin A (IgA)	Immunoglobulin G (IgG)
HbA1c			
Fasted labs			
Glucose (fasted) Week 1 and Week 13 only	Insulin (fasted) Week 1 and Week 13 only		

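### Hemoglobin has no scheduled value at Weeks 6, 8, 10 and 12, so responses first present then are dated about a week late and the Week 8 rescue cut-off has no scheduled hemoglobin

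*Protocol*

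**What the plan says.** Protocol Section 5.1 says that "study visits will occur weekly throughout the treatment period". In Protocol Section 8.1 the row "Blood chemistry and hematology" is marked at screening, at Weeks 1 to 5, then at Weeks 7, 9, 11, 13, 14, 16 and 20, and at early withdrawal. Weeks 6, 8, 10 and 12 are blank. SAP Section 3.3 shows the same pattern. Protocol Section 8.3.4 ("Laboratory sample parameters are listed below") places hemoglobin in the hematology panel. Footnote 8 to the table concerns local hematology as a back-up for hemolyzed central samples; it adds no visit.

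Blood is drawn at the four blank visits all the same. The row "RVT-1401 PK sampling" is marked at each of them, and so is total IgG, for which footnote 6 says "Two samples for IgG will be collected: one will be sent to the central lab for safety monitoring", with a further sample for the pharmacodynamic endpoint.

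Protocol Section 4 makes change in hemoglobin, time to response and "time to achieving Hb levels in the normal range" secondary objectives. Response needs a hemoglobin of at least 10 g/dL and a rise of at least 2 g/dL, "without rescue therapy or blood transfusions in the previous two weeks".

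Protocol Section 6.9.2 permits rescue in the first 8 weeks for hemoglobin below 7.0 g/dL or for listed ischemic, hypoxic or cerebrovascular signs or symptoms. It then adds: "Participants requiring rescue therapy after the Week 8 visit will be discontinued and an early withdrawal visit scheduled".

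**The concern.** Two secondary time-to-event endpoints and the by-visit change in hemoglobin all rest on a value that is measured weekly up to Week 5 and only every second week from there to Week 13, while participants attend and give blood every week. The coarser dating comes from leaving one test off existing draws, and neither document says how the wider interval is to be handled.

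The rescue rule adds a second issue. One of its triggers is a hemoglobin threshold, and what happens to the participant changes at the Week 8 visit, yet that visit has no scheduled hemoglobin. Whether a fall just before the cut-off leads to permitted rescue or to discontinuation may then depend on whether the site took an unscheduled sample. A discontinued participant may have no Week 13 value, and Protocol Section 10.3.2 analyses the primary endpoint on available data without imputation.

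**Working it through.** There is no figure in the plan to reproduce: the sample size was not derived statistically (Protocol Section 10.1). The check is a count of the schedule.

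**Reading the table.** The hematology row fills all 18 columns (screening, Weeks 1 to 14, 16 and 20 less the unused numbers, and early withdrawal) and is identical in the two documents, so a slipped column is unlikely. Of the 12 post-baseline visits from Week 2 to Week 13, 8 have a scheduled hemoglobin (2, 3, 4, 5, 7, 9, 11, 13) and 4 do not (6, 8, 10, 12). All 4 lie among the 8 visits of Weeks 6 to 13.

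**Spacing.** Taking nominal day = 7 × (week − 1) + 1, the gaps between scheduled values over Weeks 1-2-3-4-5-7-9-11-13 are 7, 7, 7, 7, 14, 14, 14 and 14 days. Visit windows are ±1 day through Week 12 and ±2 days at Week 13. A 14-day gap can therefore run from 12 to 16 days, and the last one from 11 to 17 days.

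**Dating.** I assume that an event is dated at the first scheduled visit where it is seen, and that it persists to that visit.

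| First present at | Dated at | Nominal delay against weekly testing |
|---|---|---|
| Weeks 2 to 5 | same visit | 0 days |
| Weeks 7, 9, 11, 13 | same visit | 0 days |
| Weeks 6, 8, 10, 12 | Weeks 7, 9, 11, 13 | 7 days |

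If onset is spread evenly over a span (an assumption), the mean wait to the next value is Σ(gap²/2) / Σ(gap).

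- Weeks 5 to 13, current schedule: 4 × (14²/2) / 56 = 392/56 = 7.0 days.
- Weeks 5 to 13, weekly: 8 × (7²/2) / 56 = 196/56 = 3.5 days.
- Weeks 1 to 13, current schedule: (4 × 24.5 + 4 × 98) / 84 = 490/84 = 5.8 days.
- Weeks 1 to 13, weekly: 12 × 24.5 / 84 = 294/84 = 3.5 days.

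**Rescue.** Week 7 is Day 43, Week 8 is Day 50 and Week 9 is Day 57. If hemoglobin falls below 7.0 g/dL after the Week 7 sample and before the Week 8 visit, the next scheduled value is 7 days after the cut-off visit. Three conditions must hold together for the rule to bite: the fall lies in that one week, none of the listed signs or symptoms appears, and no unscheduled hemoglobin is taken. The documents give no frequency for this. With about 16 evaluable participants planned, one participant is 1/16, or about 6%, of the total.

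**The case against.** The strongest reply is that this is a defensible choice of resolution. Hemoglobin is weekly through Week 5, and Protocol Section 3.3.2 expects the IgG nadir by the third to fifth dose, so sampling is densest where the effect should develop. From Week 6 to Week 12 the even weeks carry PK and IgG and the odd weeks carry hematology, which looks like deliberate alternation, though no reason is stated. Both cohorts share the schedule. This stands as a reason not to press the point hard; it does not explain why a test on blood already being drawn was left out.

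On rescue, weekly visits continue with vital signs (including pulse oximetry) and adverse event review, and symptoms alone can trigger rescue. Protocol Section 8.3.4 foresees extra local tests and requires recording those that change management or are clinically significant. That stands, and it makes the rescue consequence conditional. It does not help the time-to-event endpoints, because tests recorded on those grounds are not comparable across participants.

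A reader might infer more than the documents support:

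- That time to response is late in general. Only events first present at the four blank visits are affected.
- That the spacing undermines the primary endpoint. Week 13 has its own scheduled hemoglobin; the only route to that endpoint is a discontinuation.
- That Sections 6.9.2 and 8.1 contradict each other. One sets a time limit and the other sets sampling times, and both can be followed. This is a gap between rule and schedule.
- That weekly hemoglobin would end such losses. A participant who falls below the threshold just after Week 8 is discontinued under the rule whatever the sampling.

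**Conclusion.** The point holds as a modest improvement to the protocol. Four of the 12 weekly post-baseline visits to Week 13 have no scheduled hemoglobin. The interval between values doubles to 14 days after Week 5, and a response or normal hemoglobin first present at one of those visits is dated nominally 7 days late. The mean-lag figures also rest on evenly spread onset.

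The rescue effect is a possibility of unknown frequency that depends on the three conditions above. Its cost, if it occurs, is a participant who may have no Week 13 outcome.

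The practical reach is limited. SAP Section 1 records that the study was paused with 5 participants enrolled in Cohort 1, and that Version 3.0 is listings only with derived variables removed. Time to response will not be derived for Cohort 1 under that plan. The point bears on the protocol endpoints in any further enrolment or later analysis.

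**What to change.** Add hemoglobin to the blood draws already scheduled at Weeks 6, 8, 10 and 12, in Protocol Section 8.1 and in the matching SAP table. State that these values are used for change in hemoglobin, time to response and time to normal hemoglobin. Scheduled post-baseline values to Week 13 then rise from 8 to 12, the longest nominal gap falls from 14 to 7 days, and the Week 8 visit has a scheduled value.

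The cost is a small added blood volume at four visits in anemic participants. It may mean both a central and a local sample if footnote 8 applies, and the blood volume given in the consent form would need updating.

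Separately, the clinical team should reconcile the Week 8 cut-off in Protocol Section 6.9.2 with the assessment schedule. The cut-off is a clinical matter and no rule is proposed here.
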